## 4.4 Handling of Dropouts or Missing Data

MMTTs will require a minimum of two timepoints in order to be considered evaluable. Any missing timepoints will be imputed using the following rules:

For C-peptide and blood glucose values:

- If the final timepoint is missing, it will be imputed as the average of the last available timepoint and zero (the value '0'). If consecutive, final timepoints are missing, this function will be performed twice (once for each timepoint).
- If a middle timepoint is missing, it will be imputed as the average the two neighboring timepoints. If consecutive, middle timepoints are missing, both values will be imputed as the average of the two closest, neighboring values on each side.

C-peptide value only:

- If the 0 minute timepoint is missing, the value will be imputed as zero (the value '0'). If multiple timepoints were missed at the start of an MMTT, the timepoints will be imputed in reverse order (starting with the latest missing timepoint). The missing timepoint(s) will be imputed as one-half the value of the subsequent timepoint. The 0 minute timepoint will be imputed as zero (the value '0').

Blood glucose value only:

If a first timepoint is missing, the value will be imputed as the average of the first available timepoint and zero (the value '0'). If multiple timepoints were missed at the start of an MMTT, the timepoints will be imputed using this same formula, in reverse order (starting with the latest missing timepoint and repeating for each subsequent missing value until the 0 minute timepoint has been imputed).

For AE dates where the start and/or end date are partial dates, the following rules will apply:

- If a month and year of an event is clearly after implant, then the dates will remain partial dates but the AEs will be indicated as treatment-emergent.
- For partial dates within the same month and year as the implant, if the site knows the event occurred prior to implant, then they enter "01" for the day. If the site knows the event occurred after implant, then they enter the last day of the month. Using these rules, the AEs will be correctly indicated as treatment-emergent or non-treatment-emergent.

For partial dates within the same month and year as the implant, if the site does not know whether the event occurred prior to the implant, then they will be instructed to make their best estimate. For partial dates entered prior to this instruction being added to the eCRF guidelines, "01" will be imputed for the day, which will result in all such AEs being indicated as treatment-emergent.

No additional imputations will be performed for any other missing data in this study.

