### 2.2.2. Secondary Endpoint Measures

Secondary Safety and Tolerability Endpoints: The comprehensive safety profile of VC-02 combination product implanted for up to two years as measured by:

- All reported AEs
- The incidence of immune sensitization defined by presence of donor anti-HLA antibodies absent prior to implant.
- Implant tolerability assessments (e.g., fever, erythema, pain, tenderness, induration) for up to four hours post-implantation and at subsequent visits.
- The incidence of subjects requiring a premature explant due to safety, tolerability, or malfunction issues.

Secondary Efficacy Endpoints:

- Change from baseline to Weeks 16, 26, 39, 52, 78, and 104 in C-peptide AUC0-2h or AUC0-4h following an MMTT;
- Time to onset of biological response of C-peptide following MMTT;
- Percent of subjects achieving a positive stimulated C-peptide (defined as >0.2 ng/mL) after implant;
- Change from baseline to Weeks 16, 26, 39, 52, 78, 104 in weekly frequency of hypoglycemic events;
- Percent of subjects free of severe hypoglycemic events from Week 16 to Weeks 20, 26, 39, 52, 78, and 104;
- Change from baseline to Weeks 16, 26, 39, 52, 78 and 104 in Clarke score;
- Change from baseline to Weeks 16, 26, 39, 52, 78, and 104 in average daily insulin dose in the seven days preceding the Clinic Visits;
- Percent of subjects who achieve a 50% reduction in average weekly exogenous insulin dose from baseline to Weeks 16, 20, 26, 39, 52, 78, and 104;
- Percent of subjects who achieve exogenous insulin independence; of those subjects achieving insulin independence, the percent achieving HbA1c <7.0%
- Percent of time spent with blood glucose values at various cut points (e.g., <54 mg/dL, ≥54 to <70 mg/dL, ≥70 mg/dL to ≤180 mg/dL, and >180 mg/dL) as measured by each subject's CGM device.

• Change from baseline to Weeks 16, 26, 39, 52, 78, and 104 in time-in-euglycemic range (≥70 mg/dL to ≤180 mg/dL), time-in-hypoglycemic ranges (<54 mg/dL and ≥54 to <70 mg/dL), and time-in-hyperglycemic ranges (>180 mg/dL) as measured by each subject's CGM

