### 7.2. Mixed Meal Tolerance Test (MMTT)

MMTTs are conducted after all other vital signs evaluations and laboratory tests have been collected. The MMTT test should only be started if the subject has been fasting for at least eight

(8) hours. All MMTT supplies will be provided by the Sponsor or designee. Basal exogenous insulin will be continued during the test, but any short-acting insulin will be withheld starting four hours prior to starting the test. Prior to initiating the MMTT, the subject's fasting glucose will be tested at the site and the value must be within 70-200 mg/dL to begin the MMTT. If the fasting glucose is not initially within range, the site may recheck levels while the subject is still at the clinic. If the fasting glucose remains outside of the allowed range, the subject must return to the site within the visit window and attempt the MMTT again.

An intravenous catheter can be placed in a patent vein in the subject's arm for the collection of blood samples. Insertion of the catheter should occur at least 30 minutes prior to any blood collections on the days MMTTs are performed. The subject should sit upright during the test. Slow walking is permitted, but vigorous exercise should be avoided.

Baseline, fasting blood samples are drawn for glucose and C-peptide within approximately five minutes prior to the start of the meal test. At time = 0, the subject drinks Boost $\mathbb{R}$  Hi-Protein (volume equal to 6 mL/kg body weight to a maximum of 360 mL). The entire drink must be ingested within 15 minutes.

For any visits requiring both an MMTT and an explant procedure, it is acceptable to perform the MMTT on a separate day up to 5 days prior to the explant procedure. Further details regarding MMTTs may be outlined in the study reference manual.

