## 4.6.6.2 Exogenous Insulin Independence

Exogenous insulin independence will be defined in two ways.

First, achieving exogenous insulin independence is defined as having an exogenous insulin dose of 0 for a minimum of any 14 consecutive days during the study, based on the data from exogenous daily insulin dose logs. Missing or blank values on the daily insulin log are not considered to be 0 values.

The second definition of exogenous insulin independence includes having an exogenous insulin dose of 0 for a minimum of any 14 consecutive days (the first definition of insulin independence) in addition to having HbA1c  $\leq$  7.0%, and (2-hour or 4-hour) MMTT fasting (at the start of the MMTT) glucose  $\leq$  125 mg/dL and 120-minute glucose  $\leq$  180 mg/dL. The HbA1c value and the MMTT glucose values will be those values obtained at a clinic visit that is closest temporally to the 14 consecutive days of 0 exogenous insulin dose. Depending on when the 0 doses of insulin begin, it is possible that the closest value temporally for HbA1c may be from a different clinic visit than the closest value temporally for glucose from the MMTT.

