The number and percent of subjects free of severe hypoglycemic events between study visits (Weeks 16-20, Weeks 20-26, ..., Weeks 91-104, and Weeks 16-104) will each be analyzed using Fisher's exact test. The number and percent of subjects in each treatment group and the p-value from the Fisher's test will be provided (at each time point, where appropriate). These analyses will be performed using both HEs from patient-reported diary and HEs from CGM.

Change from baseline to Weeks 16, 26, 52, 78 and 104 in Clarke score will be analyzed using ANCOVA, with treatment group as a factor and the relevant baseline as a covariate. A listing of the Clarke total score will be provided.

Change from baseline to Weeks 16, 26, 39, 52, 78 and 104 in average daily insulin requirement in the seven days preceding the clinic visit will be analyzed using ANCOVA, with treatment group as a factor and the relevant baseline as a covariate. A listing of insulin dosing will be provided.

The number and percent of subjects who achieve a 50% reduction in average weekly exogenous insulin dose from baseline to Weeks 16, 20, 26, 39, 52, 78, and 104 will each be analyzed using Fisher's exact test. The number and percent of subjects in each treatment group and the p-value from the Fisher's test will be provided (at each time point, where appropriate).

The number and percent of subjects who achieve exogenous insulin independence (both definitions will each be analyzed using Fisher's exact test. The number and percent of subjects in each treatment group and the p-value from the Fisher's test will be provided (at each time point, where appropriate).

Percent of time spent with blood glucose values at various cut points at each scheduled visit will be summarized descriptively. The coefficient of variation (CV) of blood glucose values will be included in the summary. The percentages and change from baseline percentages will be summarized for each cut point (<54 mg/dL,  $\geq$ 54 to <70 mg/dL,  $\geq$ 70 mg/dL to  $\leq$ 180 mg/dL,  $\geq$ 180 mg/dL, and >250 mg/dL) and for each treatment group. The number of subjects with Prolonged HEs (duration > 120 minutes for cut points  $\leq$ 54 mg/dL and  $\leq$ 70 mg/dL) will also be summarized.

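### SAP 4.4 fills a missing first or final MMTT glucose with half its neighbour, and SAP 4.6.6.2 does not bar such values from the second insulin-independence definition, so a failed glucose limit can be recorded as met (minor).

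*SAP*

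**What the plan says.** SAP 4.4 opens its MMTT rules without restricting their use: "Any missing timepoints will be imputed using the following rules". For C-peptide and glucose alike, "If the final timepoint is missing, it will be imputed as the average of the last available timepoint and zero". For glucose only, "If a first timepoint is missing, the value will be imputed as the average of the first available timepoint and zero". A single missing middle sample is the mean of its two neighbours. A test with two observed samples is evaluable, and neither the 0-minute nor the 120-minute sample has to be one of them.

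SAP 4.6.6.2 defines insulin independence in two ways. The first is 14 consecutive days at zero insulin. The second adds HbA1c of at most 7.0%, "MMTT fasting (at the start of the MMTT) glucose" of at most 125 mg/dL and a 120-minute glucose of at most 180 mg/dL, from a 2-hour or 4-hour test. On the source of these values it says: "The HbA1c value and the MMTT glucose values will be those values obtained at a clinic visit that is closest temporally" to the zero-insulin days. Its only missing-data sentence concerns the insulin log.

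SAP 6.2 analyses both definitions with Fisher's exact test: "The number and percent of subjects who achieve exogenous insulin independence (both definitions will each be analyzed using". The protocol endpoint has no glucose limit; Protocol 2.2.2 asks only, "of those subjects achieving insulin independence, the percent achieving HbA1c" below 7.0%.

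**The concern.** Halving treats zero as a plausible next value. That has some logic for C-peptide in subjects who start with almost none, but glucose does not tend to zero before or after a meal. The two points that can be halved are the two that the second definition tests: 0 minutes is the first sample of every MMTT, and 120 minutes is the last sample of the 2-hour MMTT.

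The glucose rules also have no other evident use. SAP 4.6.1 defines AUC for C-peptide only. Apart from listings, the second independence definition is the only stated analysis that uses MMTT glucose. A programmer who applies SAP 4.4 first and SAP 4.6.6.2 second would be following the text.

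At stake is a responder count for insulin independence with glycaemic control, in a cohort of up to 60 subjects. If responders are few, one false responder would be visible.

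**Working it through.** The plan gives no figure to reproduce. The check applies the SAP 4.4 rules and compares the result with the SAP 4.6.6.2 limits.

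**Inputs.** Limits of 125 mg/dL at 0 minutes and 180 mg/dL at 120 minutes (SAP 4.6.6.2). Imputed end value = (neighbour + 0)/2; single middle value = mean of the two neighbours (SAP 4.4). Sampling at 0, 30, 60, 90 and 120 minutes, plus 180 and 240 in the 4-hour test (Protocol 7.2.1 and 7.2.2). Site fasting glucose: "fasting glucose will be tested at the site and the value must be within 70-200 mg/dL to begin the MMTT" (Protocol 7.2).

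**Passing limits.**
- 0-minute value missing: passes if the 30-minute value is at most 2 × 125 = 250.
- 120-minute value missing, 2-hour test: passes if the 90-minute value is at most 2 × 180 = 360.
- Two consecutive values missing at that end, halved twice: the 60-minute value need only be at most 4 × 125 = 500, or 4 × 180 = 720 in a 2-hour test.

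**Illustrations.** The true and neighbouring values are assumptions, since the documents give none.

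| Lost value (true) | Neighbour | Imputed | True result | Recorded |
|---|---|---|---|---|
| Fasting 126 | 30 min: 200 | 100 | fail | pass |
| Fasting 160 | 30 min: 220 | 110 | fail | pass |
| Fasting 200 | 30 min: 250 | 125 | fail | pass |
| Fasting 110 | 30 min: 260 | 130 | pass | fail |
| 120 min 200 | 90 min: 220 | 110 | fail | pass |
| 120 min 290 | 90 min: 300 | 150 | fail | pass |
| 120 min 350 | 90 min: 360 | 180 | fail | pass |

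**Direction.** For the fasting limit, a false pass needs a 30-minute rise of at most 250 − fasting: 124 at 126, 90 at 160, 50 at 200. A false fail needs a true fasting value of 125 or less and a 30-minute value above 250, so a rise above 250 − 125 = 125 at the least. For the 120-minute limit, a false fail needs a fall of more than 360 − 180 = 180 in the last half hour.

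**4-hour test.** A lone missing 120-minute value is averaged: with 260 at 90 minutes and 230 at 180 minutes it becomes (260 + 230)/2 = 245, still a fail. Halving reaches this point only if the 120-, 180- and 240-minute samples are all missing (260 would give 130).

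**Exposure.** After implantation there are seven 2-hour tests (Weeks 8, 12, 16, 20, 39, 65, 91) and four 4-hour tests (Weeks 26, 52, 78, 104). The fasting limit is exposed in all 11 and the 120-minute limit in the seven 2-hour tests. From Week 26 on, only 3 of 7 tests are 2-hour.

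**The case against.** The best reply is that SAP 4.6.6.2 speaks of values obtained at a visit and looks for the one closest in time. Read naturally, a result that was never obtained is passed over for the next-closest one. SAP 4.6.1 expressly sends missing C-peptide to the Section 4.4 rules; SAP 4.6.6.2 has no such link. This reading is possible. The SAP does not state it, however, and it leaves the glucose rules in SAP 4.4 without evident use.

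Other safeguards help less than they seem to. SAP 4.6.1 maps unscheduled samples to missing timepoints, but for AUC calculation. The pre-test site glucose in Protocol 7.2 means a measured fasting value should exist, but the SAP does not link it to the definition.

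The reply is right on scale. Protocol 7.10 expects insulin reduction typically over three to six months, so the Week 8 and 12 tests matter little. Fourteen zero-insulin days, HbA1c and the other glucose limit must still be met.

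A reader might infer more than the documents support:
- **That the error always favours the product.** The fasting 110 example is a false fail.
- **That seven of eleven tests measures the 120-minute exposure.** It overstates it, given the count from Week 26 on.
- **That the same halving inflates the primary C-peptide result.** Halving a final Week 26 sample lowers that AUC. With screening C-peptide limited to 0.2 ng/mL or less, this is conservative for the change. Gaps beyond the stated rules arguably have no AUC already, because SAP 4.4 allows no further imputation.

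**Conclusion.** The concern holds as a minor point. Nothing in SAP 4.4 or 4.6.6.2 keeps an imputed glucose out of the second insulin-independence definition, and following the rules in order can record a failed limit as met. The figures of 250 and 360 mg/dL are arithmetic limits, not frequencies. The fasting comparison assumes that the lost 0-minute sample would have been close to the site reading.

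The effect is confined to one of two definitions of one secondary endpoint. The first definition and the protocol endpoint use no MMTT glucose. SAP 6.2 treats the p-values as descriptive and SAP 4.5 says no hypotheses are tested, so the issue is the reported count. The documents give no rate of missing samples, so the number of subjects affected is unknown; it is probably small. They do not show that imputed values would certainly be used, only that the SAP does not prevent it.

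**What to change.** State in SAP 4.4 and 4.6.6.2 that only observed 0- and 120-minute glucose values count towards insulin independence. Choose the closest MMTT without regard to which samples are missing, and count the glucose criterion as not met if the required value at that test is missing. Add a sensitivity count that uses the next-closest MMTT with both values observed.

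The cost is a short SAP wording change and one extra table. The downside is that a true responder with a lost sample may be counted as a non-responder in the main count; the sensitivity count shows how many. Classing such subjects as not evaluable would also be defensible, but the SAP should make the choice before the data are seen. No change to the C-peptide rules is proposed here.

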## **10.3.2.** Internal Efficacy and Safety Review

After the last subject in Cohort 2 passes Visit 11 (Week 26), cumulative data from all Cohort 1 and Cohort 2 subjects will be assembled and sent to the DSMB and Sponsor for review. If the Sponsor believes the efficacy data appear robust, and the DSMB believes the safety data are appropriate, the Sponsor may choose to proceed to an End-of-Phase 2 (EoP2) meeting with the FDA to discuss next steps.

The Sponsor will perform a risk/benefit assessment at 9-12 months post-implant for each Cohort 2 subject and at other time points, as warranted. This assessment evaluates each individual subject's data in order to determine whether that subject should continue taking chronic immunosuppression and remain in the study or whether all units will be explanted. Factors evaluated include C-peptide concentration, histology from a sentinel device explanted at approximately nine (9) months, change from baseline in average weekly insulin administration, change from baseline in HbA1c, change from baseline in frequency of hypoglycemic events, change from baseline in Clarke Score, change from baseline in time-in--range, compliance with immunosuppression, as well as adverse events and other safety findings. In cases where a subject is early terminated from the study as a result of the risk/benefit assessment, specific early termination visit procedures (i.e., the 4-hour MMTT and safety ultrasound) will not need to be repeated if they were recently performed (within the last 8 weeks).

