## **13.6.** Reasons for Withdrawal

Investigators will make reasonable efforts to keep enrolled subjects in the study. However, if a subject is removed from treatment, a termination visit must be performed. This would generally include all procedures outlined in Visit 17 (Week 104) as well as the procedures outlined in followup Visit 18 (Week 105). Adverse events should be followed until their resolution.

Subjects may withdraw from the trial at any time at their own request, or they may be withdrawn at any time at the discretion of the Investigator or Sponsor for safety or behavioral reasons.

There are subject-specific criteria and product-related criterion that will necessitate withdrawal from the study.

- After a minimum of eight weeks post-implantation, the subject experiences three or more Severe Hypoglycemic Events (SHE) over a six-month period unrelated to anything other than VC-02. This assumes the SHE occurred despite reasonable adjustments in the exogenous insulin requirements and appropriate dietary adjustments.
- Subject has a new onset, off-target cell growth within the unit confirmed by a board-certified pathologist as a teratoma and is considered related to VC-02.
- Subject appears to mount an immune or inflammatory response that puts the subject at risk for severe or serious immune reaction AEs. In this case, the Sponsor will assess the case fully (e.g., clinically and immune test results) and advise whether an explant of any units is advisable to facilitate continued participation.
- Subject becomes pregnant or in the Investigator's opinion is non-compliant with contraception requirements (see Section 5.4.5).
- Due to the recommendation based upon the outcome of a risk/benefit assessment (see Section 10.3.2).
- Implanted units appear to be damaged or malfunctioning (e.g., localized infections, damaged unit) resulting in severe or serious AEs. Note: In the case of a suspected malfunctioning or damaged unit, the Sponsor will assess the case fully and advise whether an explant of any units is advisable. Explant of one VC-02-300 unit may occur in this situation without requiring the withdrawal of the subject from the study upon request from the Sponsor.

If a subject meets any of these criteria, the VC-02-300 units and any remaining sentinel units will be explanted. The subject will be asked to follow-up with the study site post-explant in the long-term follow-up study.

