#### **13.6.1.** Handling of Withdrawals

Subjects who are withdrawn prematurely from the study will have the VC-02-300 units and sentinels explanted. If a subject withdraws from the trial and also withdraws consent for disclosure

of future information in writing, no further evaluations should be performed, and no additional data should be collected. The Sponsor may retain and continue to use any data collected before withdrawal of consent.

If a subject does not return for a scheduled visit, every effort should be made to contact the subject. It is recommended that three (3) attempts by telephone and at least three (3) attempts by certified letter should be made to contact the subject. All attempts to contact the subject must be documented in the subject's medical record. Procedures will be put in place at each site to ensure that if a subject loses contact with the trial site, alternative measures will be utilized for the collection of information. This may include contacting family members and health care providers and, when appropriate, using subject location services. In all circumstances, every effort should be made to document the subject's outcome, if possible, and to advise the subject to return to the clinic for explantation of the VC-02-300 units and sentinels.

Subjects who have not withdrawn consent, but who have been discontinued from the main study prematurely (with products explanted) will be rolled over into a long-term, follow-up trial. Those subjects may initiate any other therapy as needed to treat diabetes and any other concurrent medical conditions.

Withdrawal due to AE should be distinguished from withdrawal due to insufficient response and recorded on the appropriate AE CRF page. When a subject withdraws due to an SAE, the SAE must be reported in accordance with the reporting requirements defined in Section 8. The reason for discontinuation will be documented in the subject's source records.

For safety reasons, all early termination procedures (including explantation procedure) as described in Visit 17/ET and Visit 18 should be performed if a subject discontinues the trial.

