#### 4.6.8 Early termination (ET) visit mapping

For safety assessments, including clinical laboratory assessments, vital signs, electrocardiogram (ECG), and physical examination, the ET visit will not be mapped. The ET data will be combined

with Week 104 data for summaries, and the time point will be displayed as "Week104/ET".

For the efficacy assessment MMTT and Clark Hypoglycemia Unawareness Score, the ET visit will be mapped to the next scheduled visit at which that data type is collected. This mapped scheduled visit data will be used for analyses and summaries.

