## 6.2 Secondary Efficacy Endpoints and Analyses

Each of the secondary efficacy endpoints will be analyzed using an  $\alpha = 0.05$  level of significance. Given the large number of secondary efficacy endpoints, the p-values for these endpoints will be considered descriptive.

For all secondary efficacy analyses, the FAS (Cohort 2 subjects who meet the FAS criteria) will be used. Change from baseline in C-peptide AUC0-4h following an MMTT at Weeks 52, 78, and 104 and change from baseline in C-peptide AUC0-2h following an MMTT at Weeks 8, 12, 16, 20, 39, 52, 65, 78, 91, and 104 will be analyzed in a similar manner to the ANCOVA performed for change from baseline in C-peptide AUC0-4h at Week 26, with the relevant baseline as the covariate. For subjects who continue to have a C-peptide  $\leq 0.1$  ng/mL as determined by the simplified oral glucose challenge test, the AUC of the respective 2-hour MMTT will be set to 0. A listing of the 2-hr MMTT/C-Peptide and Glucose results will be provided, as well as a listing of the simplified oral glucose challenge.

Time to onset of biological response of C-peptide following MMTT will be assessed using Kaplan-Meier (KM) product-limit method, with the p-value from the logrank test also provided.

The number and percent of subjects achieving a positive stimulated C-peptide (defined as > 0.2 ng/mL) after implant will be analyzed using Fisher's exact test. The number and percent of subjects in each treatment group and the p-value from the Fisher's test will be provided (at each time point, where appropriate).

Change from baseline in frequency of hypoglycemic events (24-hour; daytime [start between 6 a.m. -12 a.m.]; nocturnal [start between 12 a.m. -6 a.m.]) at Weeks 16, 26, 52, 78 will be analyzed using ANCOVA, with treatment group as a factor and the relevant baseline as a covariate. This analysis will be performed using HEs from both the patient-reported diary and from CGM. A listing of hypoglycemic events will be provided for both patient-reported data and from CGM data.

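### Second-year results labelled FAS, above all Week 104, describe only subjects still implanted after a 9-12 month decision that draws on efficacy results, and the SAP has no rule for those explanted

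*SAP*

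**What the plan says.** **The decision.** Protocol 10.3.2: "The Sponsor will perform a risk/benefit assessment at 9-12 months post-implant for each Cohort 2 subject and at other time points, as warranted". The question is "whether that subject should continue taking chronic immunosuppression and remain in the study or whether all units will be explanted". On the basis for it: "Factors evaluated include C-peptide concentration, histology from a sentinel device explanted at approximately nine (9) months". The list goes on to insulin use, HbA1c, hypoglycemic events, Clarke score, time in range, compliance with immunosuppression, and safety findings. No threshold is given.

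**Its consequence.** Protocol 13.6 lists the assessment's recommendation among the criteria that require withdrawal. Protocol 13.6.1: "Subjects who are withdrawn prematurely from the study will have the VC-02-300 units and sentinels explanted". Discontinued subjects move to a separate follow-up trial and may start other diabetes treatment.

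**The analysis.** SAP 6.2: "For all secondary efficacy analyses, the FAS (Cohort 2 subjects who meet the FAS criteria) will be used". C-peptide AUC is analysed by visit-wise ANCOVA up to Week 104, and so are Clarke score and insulin dose. Hypoglycemic event frequency is analysed the same way up to Week 78. The 50% insulin-reduction endpoint uses Fisher's exact test up to Week 104, with no stated denominator. CGM percentages are descriptive.

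**Missing data.** SAP 4.4 covers time points within an MMTT and partial AE dates, then adds: "No additional imputations will be performed for any other missing data in this study". For MMTT and Clarke score only, SAP 4.6.8 says "the ET visit will be mapped to the next scheduled visit at which that data type is collected". SAP 9.1 describes the internal review but leaves out the individual risk/benefit assessment.

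**The concern.** Whether a subject has a second-year value depends partly on the results being averaged. An ANCOVA at a single visit drops anyone without a value there. The baseline covariate cannot repair this: entry excluded stimulated C-peptide above 0.2 ng/mL, so baselines are all low and say little about who later responds. The SAP plans no repeated-measures model, non-responder rule or sensitivity analysis.

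The stake is the Cohort 2 objective of evaluating efficacy out to Month 24. The visits after Week 52 are the second-year evidence for it. A table headed FAS, in a plan that equates the FAS with intent-to-treat, will be read as covering everyone implanted in Cohort 2.

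**Working it through.** **1. The plan's own figure.** SAP 10 gives an AUC of 0.8 ng x hour/mL for a flat 0.20 ng/mL over four hours. With the trapezoidal rule of SAP 4.6.1: 4 x 0.5 x 0.20 + 2 x 1 x 0.20 = 0.40 + 0.40 = 0.80. This agrees. The power statements for n = 40 are blacked out, so nothing else can be reproduced.

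**2. Where an early-termination (ET) value lands.** Inputs: the 4-hour MMTT is scheduled at Weeks 26, 52, 78 and 104; the 2-hour MMTT at Weeks 39, 65 and 91 (and earlier); the Clarke survey at Weeks 39, 52, 78 and 104 (and earlier). Protocol 10.3.2 waives the ET 4-hour MMTT if one was done in the previous 8 weeks. Nine to twelve months is about Weeks 39 to 52.

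| ET falls | ET MMTT | MMTT counted at | Clarke counted at |
|---|---|---|---|
| After Week 39, before Week 52 | Due (last scheduled 4-hour test at Week 26) | Week 52 | Week 52 |
| After Week 52, to Week 60 | May be waived (52 + 8 = 60) | If done, Week 65; Week 78 if data type means the 4-hour test | Week 78 |
| After Week 60, before Week 65 | Due | Week 65 or 78, as above | Week 78 |
| After Week 65, before Week 78 | Due | Week 78 | Week 78 |

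No row reaches Week 91 or Week 104. Week 78 gets some Clarke scores and an occasional MMTT. Insulin, hypoglycemic event and CGM endpoints have no ET mapping.

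**3. Size, with explanted subjects at zero change.** Let f be the fraction explanted after the assessment (assumed; not in the documents). The observed-case mean is the sum over retained subjects divided by n(1 - f). The all-FAS mean is the same sum divided by n. The ratio is 1/(1 - f).

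| f | Ratio | Left of 40 | Left of 60 |
|---|---|---|---|
| 10% | 1.11 | 36 | 54 |
| 20% | 1.25 | 32 | 48 |
| 30% | 1.43 | 28 | 42 |
| 40% | 1.67 | 24 | 36 |
| 50% | 2.00 | 20 | 30 |

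This ratio depends only on how many are retained, so it would be the same if retention were random. It measures the gap between two target populations, not the strength of selection on response.

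**4. Size, against the mean had all stayed implanted.** Assume log-normal C-peptide with log-SD s, and a retention score correlated rho with log C-peptide. With Φ the standard normal distribution function and q = Φ⁻¹(f), the ratio is Φ(rho x s - q)/(1 - f). At f = 30%, q = -0.524. For s = 1.2 and rho = 0.9: Φ(1.08 + 0.524)/0.70 = 0.946/0.70 = 1.35.

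| rho | s = 0.8 | s = 1.2 |
|---|---|---|
| 0 | 1.00 | 1.00 |
| 0.3 | 1.11 | 1.16 |
| 0.6 | 1.20 | 1.28 |
| 0.9 | 1.28 | 1.35 |

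Simulation gave the same values.

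**The case against.** The case for leaving the plan alone has substance.

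- **Primary endpoint.** It is read at Week 26, before the 9-12 month decision. There are no formal hypotheses, and the secondary p-values are called descriptive. This stands. The issue is bias and labelling in secondary results, not error control. Week 26 is only largely safe, because reviews may also occur at other time points.
- **Attrition will be visible.** SAP 4 reports the number of non-missing observations, and SAP 5.1 tabulates withdrawals with reasons. This stands in part: a reader could find the loss, but the table would still be headed FAS.
- **Observed-case analysis is inferred.** No sentence says it. It follows from the bar on imputation combined with visit-wise ANCOVA, and the plan offers no other route. For the Fisher tests the denominator is simply unstated.
- **Zero change is a choice of estimand.** For C-peptide it is well grounded: the graft is gone and baseline was low. For insulin, hypoglycemic events, Clarke and CGM it is weaker, because withdrawn subjects may start other treatment. This stands and limits the fix.

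Three stronger readings are tempting. A reader might infer that the later means are means in responders. The documents do not support that, since compliance and safety also decide retention and no response threshold exists. A reader might take the factors in step 3 as proof of selection on response; they are not, as shown there. A reader might also conclude that comparisons between treatment groups are spoiled by this rule. Those groups are non-randomised unit counts chosen from accumulating data, so the contrasts were never unbiased; unequal retention would add to that by an amount the documents cannot fix.

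**Conclusion.** The concern holds, and it should be fixed. Followed as written, the plan yields Week 91 and Week 104 results, under a label equated with intent-to-treat, to which subjects explanted on the 9-12 month decision contribute nothing. Week 78 is mostly in the same position for C-peptide, less so for Clarke. Week 52 is largely protected for both by the ET mapping. Endpoints of the ever-achieved kind are less affected.

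Overstatement is probable rather than certain. Over all implanted subjects it is 1.11- to 2.00-fold for C-peptide change if 10-50% are explanted and counted as zero. Against the mean had everyone stayed implanted it is about 1.00- to 1.35-fold at 30% explanted, and there is none if retention is unrelated to C-peptide. The fraction explanted, the log-SD and the correlation are all assumptions.

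**What to change.** Amend SAP 4.4 and 6.2. None of this touches when or whether units are explanted.

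1. **C-peptide AUC.** For scheduled visits after a subject's individual withdrawal with all units explanted, add an all-FAS analysis with the value set to that subject's baseline (change = 0). Show it beside the observed-case analysis. Use a robust SE, because repeated constants would otherwise make the estimate look too precise. Do not apply the rule after study-wide termination, where zeros would say nothing about efficacy.
2. **50% insulin reduction.** Count such subjects as not achieved, with the FAS as denominator.
3. **Labels and sensitivity.** Head observed-case tables after the assessment as subjects still implanted, with the number retained per group. For insulin dose, hypoglycemic event frequency, Clarke score and CGM, give change = 0 only as a sensitivity analysis.

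The cost is SAP wording, one extra programming rule and less favourable second-year figures.
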